Appendix 1.

Green Sun Medical Pressure-Sensor Equipped Pad Clinical Validation

Substudy of the Pilot Trial Green Sun Medical Dynamic Brace

Protocol Version 1.0

14 Jan 2021

Substudy participation is optional for subjects newly enrolled in the Pilot trial. Twelve subjects at select participating sites will be enrolled.

1. BACKGROUND

Spinal orthotics (braces) are effective in preventing curve progression in patients with adolescent idiopathic scoliosis. Braces work by providing corrective forces to relevant areas of the spine, but little is known about the amount of force required, or how forces change during activities and over time in response to changes in the shape of the patient's spine and torso. Therefore, it is important to be able to accurately measure these forces over the patient's course of treatment and to understand how much variation is normal, and when variation indicates that modifications need to be made to the brace in order to optimize its effectiveness.

The GSM engineering team has developed a smart pad sensor system capable of detecting changes in force magnitude and direction, but to date, the sensor system has only been evaluated on a test fixture. The smart pad sensor system of the GSM brace captures force data in two ways: interval and conditional. As the name implies, interval sampling captures sensor data at a consistent sampling rate. The objective of the conditional sampling is to capture force data when the patient and their brace are in a consistent state. This conditional sampling allows for a much more meaningful relative measure of brace performance. A conditional sample is triggered by the donning of a brace after the brace has been off the patient. Each interval force log includes the following data: 1) timestamp 2) voltage measurements for each of eight sensors embedded in the pad, and 3) readings from a 3-axis accelerometer. Each conditional force log includes the following data: 1) timestamp, 2) voltage measurements for each of the eight sensors, 3) readings from a 3-axis accelerometer, 4) the algorithmically determined force value (FV), and 5) the algorithmically determined X-Y coordinates for an equivalent point load. The smart pad system integrates with the standard sensor system placed in all braces and the data can either be stored and downloaded by the research team at study visits, or, if the subject is participating in the optional GSM Brace Wear Mobile App substudy, the data are uploaded to cloud storage when the subject syncs with the sensor.

2. OBJECTIVE

The primary goal of this substudy is to validate the ability of a pressure-sensor equipped pad (GSM Smart Pad, smart pad) to accurately and reliably measure static and dynamic forces through a combination of lab and field testing using human subjects enrolled in the GSM Pilot study.

3. PROTOCOL

Evidence for the accuracy and reliability of the force values generated by the smart pad system will be inferred via a series of comparisons to known forces and to a gold-standard measurement system (Tekscan pressure map/I-Scan™ system) both in the lab and in field testing with patient subjects. Analyses of repeated measures within each smart pad and between smart pads will be performed.

Lab Testing Materials and Methods

Lab Testing Phase 1. Twelve smart pads will be fabricated for testing and serialized in order to track performance over time. A benchtop test fixture will apply loads of 100N, 110N, 136N and 150N maintained for five minutes each with a 0-N dwell of 5 minutes in between loads. Loads will be applied in four rotational positions: neutral, 10-degree rotation from neutral, 20-degree rotation from neutral, and 30-degree rotation from neutral. Each of the 16 unique loading scenarios (magnitude x direction) will be run 10 times. The average force value under each of these conditions will be saved and analyzed. These 12 smart pads will then be used in field testing.

Lab Testing Phase 2. The smart pads removed from the brace at the 30-day follow-up visit will undergo repeat testing on the bench test fixture under the same 16 loading conditions.

Field Testing Materials and Methods

Subjects

Twelve subjects will be recruited from multiple sites to participate in the field testing. We will draw from the pool of patients who have consented to participate in the GSM Brace Pilot study. They will be told that participation in both studies is completely voluntary. Enrolled subjects may choose to stop participating at any time.

Visits and Procedures

Subjects in the substudy will undergo all procedures/assessments as those in the Pilot study. Participation in the substudy will last for approximately 1 month. One additional study visit will be required at approximately 1 month after Baseline. Otherwise, substudy procedures will

occur coincident with the Baseline, 1-week and 3-month follow-up visits in the Pilot protocol.

Baseline Visit. Subjects in the substudy will receive a GSM brace that includes one of the serialized smart pads tested during Lab Testing Phase I. No additional procedures or assessments for the substudy occur at this visit.

Visit 2 (1-2 weeks after Baseline). Substudy procedures will add approximately 1 to 1.5 hours to the total duration of this study visit. The following procedures/assessments will take place in addition to the Pilot study activities (in-brace x-ray, safety check):

1. Calibration of the pressure map. The Tekscan pressure map is a very thin, flexible material embedded with force sensors to measure the magnitude and distribution of force exerted over an area. This map must be calibrated prior to use. To calibrate the map, the orthotist and research team will establish the area where the brace's thoracic pad would contact the subject's torso. The pressure map is then placed against the subject's torso with the smart pad (not yet attached to the brace) is centered over the map. A handheld force gauge (Mark 10 Series 4) is pressed on the smart pad to successively apply 80-N and 120-N forces to the patient for a period of less than 1 minute each. These known forces are then used by the I-Scan™ system to calibrate the pressure map for subsequent readings.
2. The smart pad is then placed in the GSM brace. The subject will don (put on) the brace, and the research team will place the pressure map between the subject's torso and the smart pad. The orthotist will assist the subject to adjust the strap tension and position of the brace. The subject is then asked to stand for 5 minutes in a normal posture with minimal spinal flexion or extension.
3. The subject will then be asked to doff (remove) the brace for 5 minutes.
4. Steps 2-3 are repeated for a total of four don-doff trials. During these trials, both the pressure map and the smart pad will capture force data. The smart pad will capture interval data once per minute; the don and doff trials will trigger the algorithm to capture one conditional sample for each trial.

Interim Between Visit 2 and the 1-Month Visit. The subject will continue to wear the GSM brace with the smart pad for a period of approximately 30 days. During this time, the smart pad will continuously capture data. These data will be stored on the device and transmitted to the cloud when the device is paired with the GSM mobile app (if the subject is also participating in the optional GSM Brace Wear Mobile App study). If the subject does not pair with the device during this period, the data will be retrieved by the research team at the 1-month visit.

1-Month Visit (substudy subjects only). The smart pad will be removed from the subject's brace for Lab Testing Phase II and a replacement smart pad will be installed. The same set of

procedures completed during Visit 2 will be repeated (calibration of the Tekscan pressure map system via application of known 80-N and 120-n forces, data collection during donning and doffing). This visit will last approximately 1-1.5 hours.

4. RISKS

Subjects in the substudy should experience no additional risks beyond those encountered during participation in the Pilot study. The same safety and performance checks will be completed (e.g. if a subject does not have adequate correction in the GSM brace, or is unable to wear the brace the recommended number of hours, then the subject will exit the Pilot and the Validation substudy).

Tekscan pressure maps and the sensors embedded in the smart pad have been used in both lab and field tests without safety concerns. Applying forces of 80-N and 120-N should not cause the subject any discomfort as similar forces are applied by a typical scoliosis brace during normal wear. However, if a subject complains of discomfort, the team will withdraw the pressure immediately.

The data offloaded from the Tekscan pressure map/I-Scan™ system and the smart pad will be tagged only with the subject's study ID but no direct identifiers. These data will be treated with the same confidentiality measures as data from the Pilot study.

5. BENEFITS

The subjects in the substudy will experience no direct benefit from participating. However, we hope their participation will lead to a sensor pad-based pressure monitoring system that can be used to optimize scoliosis brace treatment in the future.

6. COSTS

Subjects in the substudy may incur uncompensated costs associated with the longer Visit 1 duration and the additional 1-month visit. These costs are in addition to those already incurred by participation in the Pilot study (e.g. travel, parking, loss of work/school time).

7. COMPENSATION

Subjects will be compensated \$50 for their participation in the 1-month substudy visit.

8. SAMPLE SIZE CALCULATIONS AND STATISTICAL ANALYSIS

No formal sample size/power calculations were done to arrive at the sample of 12 subjects. Given the large number of repeated measures data to be collected, and given the results from earlier bench work, we anticipate data from 12 subjects are adequate to attain the precision necessary to make informed decisions about the accuracy and reliability of the sensors in this study.

Lab Testing Analysis: The distribution of force values generated by each smart pad unit under each scenario will be characterized by the mean, standard deviation and coefficient of variation (CV, $((\text{mean}/\text{s.d}) * 100)$).

1. The inter- and intra-unit reliability of the force measures will be inferred by testing the variation of the means and the Csv within and between the 12 smart pad units under each of the 16 scenarios using the R package cvequality (Version 0.1.3; Marwick and Krishnamoorthy 2019) and repeated measures ANOVA. The quality control standard will be set at a CV of 5% or less. Units that demonstrate Csv >5% will not be used in the field testing.
2. Reproducibility/durability of smart pad measurements will be assessed using repeated measures ANOVA comparing Test 1 to Test 2 measures.

Field Testing Analysis

1. The force values measured by the I-Scan system and the smart pad during the Baseline and 1-Month visits will be compared using repeated measures analysis of variance.
2. The means and Csv of the force values over the 30-day wear period will be evaluated, looking for changes over time, and within and between Active and Rest periods using repeated measures ANOVA.
3. A regression model will be derived to convert each 24-hour set of force values to an estimate of the number of hours the brace was worn, using the temperature monitor output as the gold standard. The predictive accuracy of the smart pad model will be assessed using calibration plots and other error estimates.

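### Optional substudy: smart pad reliability is to be inferred from tests of equal CVs and equal means, which do not measure repeatability or agreement between pads

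*Combined protocol and SAP*

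**What the plan says.** Appendix 1 section 2 sets the substudy's goal as showing that the smart pad can "accurately and reliably measure static and dynamic forces".

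For the bench phase, section 3 states: "Twelve smart pads will be fabricated for testing and serialized in order to track performance over time". Four loads (100, 110, 136 and 150 N) are crossed with four rotations, and "Each of the 16 unique loading scenarios (magnitude x direction) will be run 10 times".

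Section 8, Lab Testing Analysis, first says that each pad's readings in each scenario will be described by mean, SD and CV. Item 1 then gives the route to the conclusion: "The inter- and intra-unit reliability of the force measures will be inferred by testing the variation of the means and the Csv within and between" units (all 12), separately in each scenario, "using the R package cvequality" and repeated measures ANOVA. The same item adds an absolute limit, "The quality control standard will be set at a CV of 5% or less", with one consequence: "Units that demonstrate Csv >5% will not be used in the field testing".

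The section gives no alpha, no rule for what follows from rejecting or not rejecting either test, no variance component or intraclass correlation, and no between-pad difference regarded as acceptable. It prints the CV as mean divided by SD.

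**The concern.** Intra-unit reliability asks how closely one pad repeats itself. Inter-unit reliability asks how closely different pads agree under the same load. Both are questions of size. The plan answers them with two tests of equality.

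The CV test asks whether all pads are equally noisy. Twelve very noisy pads satisfy that null, and so do twelve pads that disagree on force but have the same relative scatter. Twelve good pads whose small CVs differ violate it. The ANOVA on means does address agreement, but a significance verdict depends on within-pad noise as well as on the disagreement. With no acceptable difference stated, it cannot say whether a difference matters.

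What is at stake is the reliability statement that the bench phase is meant to deliver. Each field subject wears one of the serialized pads, so differences between pads coincide with differences between subjects. The size of the between-pad component is therefore worth knowing, with its uncertainty.

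**Working it through.** **Inputs from Appendix 1.** 12 pads (section 3); 10 runs per pad per scenario (section 3); 16 scenarios (section 3); CV limit 5% (section 8). The plan states no power, alpha or reliability figure for this analysis, so there is none to reproduce.

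**Assumptions.** Alpha 0.05, normal errors, one scenario at a time, CV taken as SD/mean. The true CVs and pad means below are illustrative, since the results of the earlier bench work are not given.

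**1. CV-equality test.** The plan names the package but not the test within it. I used the asymptotic chi-square statistic. With c_i the sample CV of pad i and C their average,

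T = Σ (10 − 1)(c_i − C)² / [C²(0.5 + C²)], compared with chi-square on 11 df (critical value 19.68).

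Simulated rejection rates (20,000 to 40,000 replicates):

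| True state of the 12 pads | Rejects |
|---|---|
| All CV 2% | 0.06 |
| All CV 20% | 0.06 |
| Means 80–120 N at one load, all CV 2% | 0.06 |
| CVs evenly 2% to 4% | 0.52 |
| CVs evenly 1% to 3% | 0.92 |
| CVs evenly 1% to 4% | 0.99 |

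The first three rows cannot be told apart, although only the first describes reliable pads. In the last three rows every true CV is within 5%. For 1% to 3%, all 12 sample CVs also fall within 5% in 99.6% of sets. For 1% to 4% that figure is 79%, because a pad with true CV near 4% can exceed 5% by chance in 10 runs. A likelihood-ratio version gives the same pattern: about 0.10 under equal CVs (somewhat liberal), 0.12 at CV 20%, 0.09 for 80–120 N and 0.97 for 1% to 3%.

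**2. ANOVA on pad means.** Let σ_b be the between-pad SD and σ_w the within-pad SD, both as a percentage of the load. With random pad effects the F ratio is distributed as (1 + 10σ_b²/σ_w²) × F(11, 108), and the 5% critical value is 1.878.

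| σ_b | σ_w | 1 + 10σ_b²/σ_w² | 1.878 / factor | P(significant) |
|---|---|---|---|---|
| 1% | 1% | 11.0 | 0.171 | 0.999 |
| 1% | 4.9% | 1.416 | 1.326 | 0.22 |
| 2% | 4.9% | 2.666 | 0.705 | 0.73 |
| 3% | 4.9% | 4.748 | 0.396 | 0.96 |

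The first two rows have the same disagreement between pads and opposite likely verdicts. By simulation, pad means of 99–101 N at CV 1% are called different 99.9% of the time, and means of 80–120 N at CV 2% essentially always. A significant result therefore does not separate a trivial spread from an important one.

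This takes the ANOVA as a test of pad means. If the repeated measures model treats pad as the subject, the pad effect becomes the blocking term and is not normally tested, so the model needs to be specified.

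**3. The 5% rule.** At true CV 10% a pad exceeds the limit in one scenario with probability 0.99, and at 20% with probability about 1.00. It is an absolute limit and it works, provided that CV means SD/mean. As printed, a pad with SD 2% of its mean scores (1/0.02) × 100 = 5000.

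**4. What estimation gives.** For the same simulated sets, variance components separate the cases: all pads at CV 20% give a total CV of about 20.2%. Means of 80–120 N at CV 2% give a between-pad CV of 13.1% and a total of 13.3%. CVs of 1% to 3% with no true difference in means give a total of 2.1%.

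**The case against.** The strongest reply is that the plan should be judged as a whole, and most of it stands.

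- A reader might infer that good pads are discarded and bad pads used. The documents do not support this. The CV test excludes no pad. Only the 5% rule does, and it removes pads that are all equally noisy.
- A reader might infer that pads disagreeing on force go unnoticed. The ANOVA finds an 80–120 N spread essentially every time, and a 3% between-pad SD 96% of the time even at within-pad CV 4.9%. The 22% figure concerns a 1% SD, and missing that may do little harm.
- The 92% to 99% rejection rates might be read as inflated type I error. They are power: the CVs truly differ and the test says so correctly. The fault is that the hypothesis tested is not the question asked.
- The plan does not say that rejection means a report of unreliable pads. It gives no alpha and no consequence.
- Pad means, SDs and CVs per scenario are already planned, so the spread of pad means could be read from the output.
- The field comparison with the pressure map is paired within subject, so it does not simply pool forces across pads.

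What survives is narrower. Item 1 names the tests as the basis for inferring reliability, no between-pad limit is set, and no summary of between-pad variation with its uncertainty is planned. Running 16 scenarios adds chance findings (1 − 0.95^16 = 0.56 if independent at an assumed 5%), but the point does not rest on that figure.

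**Conclusion.** The point holds as a matter of inference, not of pad selection. The CV-equality test cannot distinguish uniformly good from uniformly poor pads (about 6% rejection in both cases) and usually rejects for good pads whose small CVs differ (92% to 99% in the wider spreads examined, about 52% for 2% to 4%). The ANOVA adds real information on large disagreement, but its verdict moves with within-pad noise and has no margin to be read against. The likely result is a reliability statement that is uninformative or misleading.

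This rests on the assumed alpha of 0.05, normal errors, the illustrative CVs and the asymptotic form of the CV test. The nature of the null hypothesis does not depend on any of these. The scope is the bench phase of an optional substudy: no primary aim of the pilot and no participant safety rule depends on it. It does bear on that substudy's own primary goal, and the remedy is nearly free, so the change should be made. Accuracy against the applied load is a separate question that this point does not settle.

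**What to change.** In Appendix 1 section 8, Lab Testing Analysis:

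1. Correct the CV to (SD/mean) × 100 and keep the 5% screen.
2. Base the reliability conclusion on a random-effects model fitted to the Phase 1 data, with scenario fixed and with pad, pad-by-scenario and run residual as random terms.
3. For intra-unit reliability, report the within-pad repeatability CV with a 95% CI against the 5% standard.
4. For inter-unit reliability, report the between-pad CV with a 95% CI, and the range of pad means at each load.
5. State in advance what between-pad difference is acceptable. The plan sets none. Its 5% figure is a limit on each unit's CV, so using 5% here would be a new choice and should be justified as one.
6. Keep the CV-equality test and the ANOVA as descriptive only, with the ANOVA model specified.

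The cost is a change of wording and one mixed model on data already planned, with no new testing and no burden on subjects. The downside is imprecision: with 12 pads (11 df), and within-pad noise ignored, the 95% limits for a between-pad SD are about √(11/21.92) = 0.71 to √(11/3.816) = 1.70 times the estimate. That interval should be reported openly.

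### The smart pad substudy prints the coefficient of variation upside down, so its 5% pad acceptance rule as written would reject every pad

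*Combined protocol and SAP*

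**What the plan says.** Appendix 1, Section 8, Lab Testing Analysis, summarises the force values of each pad under each loading scenario by the mean, the s.d. and the CV. It prints the CV with the mean in the numerator and the s.d. in the denominator: "coefficient of variation (CV, $((\text{mean}/\text{s.d}) * 100". This is the only definition of the CV in the document.

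The first numbered item after it sets the limit, "The quality control standard will be set at a CV of 5% or less", and states the consequence: "Units that demonstrate Csv >5% will not be used in the field testing".

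Field Testing Analysis in the same section uses the term again without redefining it: "The means and Csv of the force values over the 30-day wear period will be evaluated". It looks for change over time and for differences within and between active and rest periods.

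The bench conditions are in Appendix 1, Section 3, Lab Testing Phase 1: "A benchtop test fixture will apply loads of 100N, 110N, 136N and 150N maintained for five minutes each", at four rotational positions, and "Each of the 16 unique loading scenarios (magnitude x direction) will be run 10 times". That paragraph closes with "These 12 smart pads will then be used in field testing".

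**The concern.** A coefficient of variation is the s.d. divided by the mean, and a small value means good repeatability. The printed ratio is the inverse, so a small value means poor repeatability. An upper limit of 5% suits the first quantity and makes no sense for the second.

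Two uses are at stake. The first is the screening of pads before field testing, where the rule as printed ranks pads in the wrong order. The second is the comparison of CVs over 30 days of wear. There is no limit there to make a wrong value look absurd. If the printed ratio were computed and read as a CV, steadier force readings would appear as greater variability.

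**Working it through.** **Inputs**
- Printed definition: 100 × mean/s.d. (Appendix 1, Section 8).
- Limit: 5% or less, per pad and scenario (Appendix 1, Section 8).
- Loads: 100, 110, 136 and 150 N; 4 loads × 4 positions = 16 scenarios; 10 runs each (Appendix 1, Section 3).
- Assumption: a pad's mean reading is close to the applied load. Only the newton figures depend on this; the percentages do not.

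The 5% is a chosen limit with no derivation behind it, so there is no figure of the plan to reproduce.

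**Step 1. What s.d. meets the limit under each definition?**
- Standard CV: 100 × s.d./mean ≤ 5 gives s.d. ≤ 0.05 × mean.
- Printed ratio: 100 × mean/s.d. ≤ 5 gives s.d. ≥ 20 × mean.

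**Step 2. Can ten readings have so large an s.d.?** For n non-negative values with mean m, the sum of squares is at most (nm)². The sum of squared deviations is therefore at most n²m² − nm² = n(n−1)m². Dividing by n−1 and taking the root gives s.d. ≤ √n × m. With n = 10, this is 3.162 × m.

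| Load (N) | Standard CV: s.d. at most (N) | Printed ratio: s.d. at least (N) | Largest possible s.d., 10 runs (N) |
|---|---|---|---|
| 100 | 5.0 | 2000 | 316 |
| 110 | 5.5 | 2200 | 348 |
| 136 | 6.8 | 2720 | 430 |
| 150 | 7.5 | 3000 | 474 |

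The lowest score the printed ratio can give is 100/√10 = 31.6%. With the n-denominator s.d. the bound is √(n−1) = 3, and the lowest score is 100/3 = 33.3%. Both exceed 5% in every scenario, so no pad can pass.

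**Step 3. How does the printed ratio rank pads?** Printed score = 100/(CV as a fraction).

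| True CV | Printed score | Under the intended rule |
|---|---|---|
| 2% | 5000% | passes |
| 5% | 2000% | passes, at the limit |
| 10% | 1000% | fails |

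The most repeatable pad scores furthest from the limit, so the order is fully reversed.

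**The case against.** The strongest reply is that nobody would be misled. The section uses the standard name, sets an upper limit and names an R package, cvequality, for testing CVs; all three point to s.d./mean. The garbled plural of CV in the same section suggests careless typing. Nothing shows that the inverted ratio would be computed. If it were, the lab step would reject every pad, and that step comes before any 30-day data exist. The slip would then be found before it could affect the field analysis. The substudy is also optional and has only 12 subjects.

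Most of this stands as a limit on the consequences. The intent is recoverable, and undetected use in the field analysis is unlikely. It would require the printed ratio to be used there although the lab step had not exposed it, and the result then to be read as an ordinary CV. The reversed reading is a possibility, not a prediction.

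It does not rescue the text. The printed formula and the 5% limit cannot both stand, and correct code would contradict the written plan. A misreading by the PDF extraction is unlikely, because numerator and denominator are both legible.

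It is also fair to say that the closing sentence of Lab Testing Phase 1, which sends the 12 pads on to field testing, does not contradict Section 8. It reads as the default, with the 5% rule as the exception.

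**Conclusion.** The concern holds. The CV is printed as its reciprocal, and the acceptance rule built on it is wrong as written: passing needs an s.d. of at least 20 times the mean, while the lowest attainable score is 31.6%. That floor assumes non-negative readings and an s.d. taken over the 10 run averages for each pad and scenario, which is the natural reading of Sections 3 and 8.

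It is very probably a drafting slip for s.d./mean. The effect is confined to the substudy's pad screening and its CV summaries. The pilot endpoints, the ANOVA comparisons of means and the regression for hours of wear do not use the CV and are unaffected. It should be corrected because a wrong formula sits behind a stated decision rule.

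**What to change.** In Appendix 1, Section 8, replace the formula with CV = (s.d./mean) × 100. State that the 5% standard and every CV analysis, both lab and 30-day, use that quantity, and confirm that the analysis code does so.

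As a minor conforming edit in Appendix 1, Section 3, make the closing sentence of Lab Testing Phase 1 refer to the pads that meet the Section 8 standard. A sentence on what happens if fewer than 12 pads pass would be a useful option, but it is not part of this error.

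The cost is one formula, one qualifying clause and a check of the code, with no new data.

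### Pressure-pad substudy: all 12 bench-tested pads are committed to 12 subjects, yet pads with CVs above 5% are barred, no qualified spare is described, and the way 16 CVs make one decision is not stated.

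*Combined protocol and SAP*

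**What the plan says.** All references are to Appendix 1, the optional substudy.

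- **Supply and use of pads (section 3, Lab Testing Phase 1).** "Twelve smart pads will be fabricated for testing and serialized in order to track performance over time". After the bench work, "These 12 smart pads will then be used in field testing".
- **Subjects (opening paragraph and section 3, Subjects).** "Twelve subjects at select participating sites will be enrolled", and again "Twelve subjects will be recruited from multiple sites to participate in the field testing". The Baseline Visit paragraph has each subject's brace carry one of the serialized Phase 1 pads.
- **Bench design (section 3).** "A benchtop test fixture will apply loads of 100N, 110N, 136N and 150N", in four rotational positions. "Each of the 16 unique loading scenarios (magnitude x direction) will be run 10 times".
- **Quality rule (section 8, Lab Testing Analysis).** A mean, an s.d. and a CV are computed separately for every pad in every scenario, and the formula printed for the CV is the mean divided by the s.d., times 100. The standard is a CV of at most 5%, and "Units that demonstrate Csv >5% will not be used in the field testing".
- **Other pads (section 3, 1-Month Visit).** A replacement pad is fitted when the first is removed for repeat bench testing. The number, source and bench testing of these replacements are not stated.
- **Sample size (section 8).** No calculation was done. Twelve subjects are judged adequate on the strength of the repeated measures and earlier bench results, which are not shown.

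**The concern.** Two statements about the same 12 pads cannot both hold if any pad fails: section 3 sends all of them to the field, and section 8 withholds the failures. With 12 subjects, 12 pads, and each subject due a Phase 1 pad, there is no slack.

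The exclusion rule is also incomplete. A pad produces 16 CVs, each an estimate with 9 degrees of freedom, and the text does not say whether one CV over the limit fails the pad, or whether the CVs are averaged or pooled. There is no allowance for sampling error or for 16 comparisons per pad. The choice of reading can move the rejection rate from almost nothing to most pads on the same data, so leaving it open until the bench results are seen gives avoidable discretion over which pads are used.

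Field testing is the substudy's only on-body evidence. If pads fail, either that sample shrinks below the 12 on which section 8 relies, or the rule is set aside as a deviation.

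**Working it through.** The plan states no pass rate or power, so the only figure to reproduce is the scenario count: 4 loads × 4 positions = 16, which agrees.

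**Step 1. The conflict, without assumptions.** Phase 1 pads made: 12. Subjects who must each receive one: 12. Spares: 12 − 12 = 0. If k pads are rejected, 12 − k subjects can be supplied, so k = 1 already breaks the stated sample.

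**Step 2. Inputs for the rejection rate.**
- From the plan: 10 runs per scenario (9 df), 16 scenarios, limit 5%, 12 pads.
- Assumed: CV = s.d./mean; normally distributed runs; one true CV, c (in %), in all 16 scenarios; independent scenarios and pads; a pad fails if any CV exceeds 5%. The documents give no value for c, so a range is shown.

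**Step 3. Formulas.**
- One scenario: p = P(χ² with 9 df > 9 × (5/c)²). The exact non-central t form agrees to within 0.001.
- One pad: R = 1 − (1 − p)^16.
- At least one of 12 pads lost: 1 − (1 − R)^12.

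For example, at c = 4 the χ² cut-off is 9 × 1.5625 = 14.06, so p = 0.120 and R = 1 − 0.880^16 = 0.871.

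| True CV | p, one scenario | R, one pad | Expected usable of 12 | At least one pad lost |
|---|---|---|---|---|
| 2.5% | 0.00004 | 0.06% | 11.99 | 0.8% |
| 3% | 0.0030 | 4.6% | 11.4 | 44% |
| 3.5% | 0.0311 | 39.7% | 7.2 | 99.8% |
| 4% | 0.1201 | 87.1% | 1.6 | about 100% |

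R passes 50% at a true CV of about 3.6%.

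**Step 4. Sensitivity at a true CV of 4%.**
- Correlated scenarios, any-scenario rule (simulation): R falls from 87% to about 68%, 43% and 12% at correlations of 0.5, 0.8 and 1.
- Pooled CV (root mean square of the 16, 16 × 9 = 144 df): P(χ² with 144 df > 144 × (5/4)²) = 0.00002.

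**Step 5. What a pooled rule gives up.** Consider a pooled limit of 5% with a single-scenario limit of 5 × √(χ² quantile with 9 df at 1 − 0.05/16, divided by 9) = 8.31%. Take a pad with true CV 6% at all four loads in one rotation and 3% in the other 12 scenarios.
- Its pooled true CV is √((4 × 36 + 12 × 9)/16) = √15.75 = 3.97%, so the pooled limit hardly ever stops it.
- It clears the 8.31% limit in every scenario with probability about (1 − 0.045)^4 = 0.83. The 3% scenarios contribute almost nothing, and simulation also gives 83%.
- Under the any-scenario 5% rule it passes with probability (1 − 0.715)^4 × (1 − 0.0030)^12 = 0.006, or 0.6%.

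**Step 6. The printed formula.** Read literally, a pad whose s.d. is 5% of its mean scores (1/0.05) × 100 = 2000. A score of 5 or less would need an s.d. at least 20 times the mean, so every working pad would fail. Steps 2 to 5 therefore use s.d./mean.

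**The case against.** The rejection rates depend on choices that the plan does not make. Section 8 never says that one CV over the limit fails a pad; averaging or pooling removes most of the effect. No true CV is given, and the earlier bench work may have shown pads well under 3%, where rejection is rare. Correlation between scenarios would lower the rates further. A strict rule can also be deliberate: detecting changes in the direction of force is a purpose of the pad, so failing a unit that is erratic in one rotation is reasonable quality control, and Step 5 shows how much a pooled rule would let through. Finally, this is an optional substudy of a pilot, and more pads will exist for the 1-month visit.

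Most of this stands, and it limits the point. A reader might infer that the rule rejects most pads that truly meet the standard. The documents do not support that: it needs the any-scenario reading, a true CV above about 3.6% and scenarios that are not strongly correlated. Nor do they show that 12 qualified pads cannot be supplied, since at a true CV of 3% all 12 survive with probability 56% even under the strict reading, and at 2.5% with probability 99%.

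What the objection does not remove is the conflict between sections 3 and 8 or the missing decision rule. The 1-month replacements do not close the gap as written, because nothing says that they are bench-qualified or available for a failed Phase 1 pad.

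**Conclusion.** The point holds as an internal conflict and an incomplete rule. One rejected Phase 1 pad makes the stated 12-subject field test undeliverable; this needs no statistical assumption. How likely that is cannot be fixed from the documents. Under the any-scenario reading, with independent scenarios and a common true CV, at least one of 12 pads is lost with probability 0.8% at a true CV of 2.5%, 44% at 3% and 99.8% at 3.5%. Correlation between scenarios or pooling of the CVs would reduce these figures. The inverted CV formula is a separate error in the same paragraph and should be corrected with it. The matter is worth settling before bench testing starts; it concerns only the substudy and does not touch the main pilot's endpoints.

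**What to change.** 1. **Reconcile sections 3 and 8.** Either bench-qualify some additional pads in Phase 1, for example from the replacements already needed at the 1-month visit, so that a rejected unit can be replaced; or restate the field sample, there and in the opening paragraph of Appendix 1, as up to 12 units that pass. The first option costs fixture time: 160 runs × (5 minutes of load + 5 minutes of dwell) = 1,600 minutes, about 27 hours per pad. The second costs only wording, but section 8's statement that 12 subjects are adequate should then be revisited.
2. **State before bench testing how the 16 CVs give one decision**: any scenario, average or pooled. A pooled CV with a higher single-scenario limit (about 8.3%) is an option for the sponsor to weigh, not a required change. It protects conforming pads from chance rejection, but it would pass about 83% of pads with true CV 6% in one rotation and 3% elsewhere, against 0.6% under the any-scenario rule.
3. **Correct the CV formula** to s.d. divided by mean, times 100.

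Items 2 and 3 are changes of wording in the substudy protocol and add no burden for subjects.
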